8.2 Determination of Sample Size

Up to 10 subjects who meet the requirements for inclusion will be enrolled in this study. No formal hypothesis testing is proposed in this study; all summary measures, including p-values, are considered descriptive.

8.3 Analysis Sets

The following analysis sets will be defined:

Full Analysis Set

The FAS will include all subjects who received any amount of IMP.

PK Analysis Set

The PK Analysis Set will include all available sebelipase alfa serum concentration data for subjects who received at least one complete infusion of IMP in this study.

8.4 Demographics and Baseline Characteristics

Demographics and baseline characteristics will be listed for each subject and tabulated.

8.5 Subject Disposition

Data from all subjects who are consented will be included in the summary of subject disposition. The frequency and percentage of subjects who are consented for, treated in, discontinued from, and complete the study, along with reasons for discontinuation, will be summarized.

8.6 Study Treatment Usage and Compliance

Number of weeks in the study and number of study infusions received by subjects will be summarized. The number (percent) of subjects who receive all study infusions 'per protocol' up until the time of last dose (i.e., subjects without missed infusions, infusion interruptions, or rate changes) will be provided. A listing of sebelipase alfa exposure by subject will be provided, including date of first dose and total number of doses (by dose level).

8.7 Efficacy Analysis

Efficacy will be analyzed for the Full Analysis Set.

Survival will be analyzed as the proportion of subjects surviving to 12, 18, and 24 months of age. As a complementary analysis, Kaplan-Meier survival curves of survival since birth and survival since first dose of IMP will be presented. Median age at death will also be calculated. A Kaplan Meier estimate of median survival past first dose of IMP will be computed.

Estimated survival rates and median age at death derived from this study will be compared to rates/times reported in the literature, and will be discussed in conjunction with information derived from previous studies.

Anthropometric indicators of growth, standardized by age and gender in accordance with the methodology described by the WHO and using WHO growth charts will be listed by study time point as observed values and as changes from baseline. Change from baseline in anthropometric data will be provided as graphs, and also tabulated as continuous data. In addition, the percentages of subjects who meet criteria for underweight, stunting, and wasting will be tabulated for each timepoint.

Change and/or percent changes from baseline in AST, ALT, and serum ferritin will be presented graphically (and tabulated) for each evaluation timepoint.

A subject will be considered to have achieved transfusion-free hemoglobin normalization (TFHN) if the subject meets all of the following criteria:

- 1. Has two post-baseline measurements of hemoglobin at least 4 weeks apart that are both above the age-adjusted lower limit of normal (LLN)
- 2. Has no known additional measurements of hemoglobin that are below the age-adjusted LLN during the (minimum) 4-week period; and
- 3. Had no transfusions during the (minimum) 4-week period, and also no transfusions for 2 weeks prior to the first hemoglobin measurement in the (minimum) 4-week period

If all 3 criteria are met, the subject will be considered to have achieved TFHN on the date of the first hemoglobin assessment in the 4-week period. The proportion of subjects who achieve TFHN will be summarized and, if sufficient data are available, a summary of time to TFHN will be created.

A subject who is transfusion-free beginning at Week 6 will be considered to have maintained transfusion-free normal hemoglobin if, regardless of baseline hemoglobin value, the subject has no abnormally low hemoglobin values beginning at Week 8 of the study and continuing for at least 13 weeks (3 months). The proportion of subjects who have maintained transfusion-free normal hemoglobin will be summarized.

The Denver II screens children's performance in four developmental domains: personal-social, fine motor-adaptive, language, and gross motor with respect to the age-matched population. DDST II results are expressed as Normal, Abnormal, Questionable, and Untestable. Denver II results will be listed.

8.8 Safety Analysis

Safety will be analyzed for the FAS.

8.8.1 Adverse Events

All reported AEs will be listed from the date of written informed consent until the end of participation in this study. Separate listings of deaths, SAEs and IARs will also be provided. The numbers and percentages of subjects experiencing any AE, any SAE, any IAR, any related AE, any related SAE, and discontinuations due to an AE will be tabulated.

The frequency of subjects with treatment-emergent AEs, SAEs, and IARs by system organ class (SOC) and preferred term (PT) (coded using Medical Dictionary for Regulatory Activities [MedDRA®] version 14 or higher) will be tabulated. Frequencies will also be presented by the classifications of severity and causality. In addition, frequency of subjects with AEs, SAEs, and IARs will be presented for time periods spanning the entire course of treatment with sebelipase alfa: from the start of dosing with sebelipase alfa in this study to 3 months after the first dose, >3 to 6 months, >6 to 12 months, >12 to 18 months, >18 to 24 months and >24 months. As appropriate, additional listings, summary tables and graphics will be generated to evaluate IAR frequency and severity over time. A listing of subjects who withdraw from the study due to AEs will be presented, and the incidence of AEs leading to study discontinuation will be summarized.

8.8.2 Clinical Laboratory Tests

Observed measurements and changes from baseline to each study timepoint in clinical laboratory data will be summarized. Clinically significant abnormal values will be listed. Frequencies of abnormal values relative to the laboratory normal range and clinically significant abnormal values will be tabulated for each study timepoint. Shift tables may also be provided.

Time to ADA positivity, median and peak antibody titer, and time to peak antibody titer; antibody titer values will be tabulated at each study visit using summary statistics appropriate to the data.

8.8.3 Other Safety Data

Changes in vital signs from pre-infusion values to each time point during or post-infusion will be summarized. Abnormal findings/values for physical examinations, vital signs, and ECGs will also be listed.

Concomitant medication/treatment data will be coded using the WHO-DRUG dictionary. All data will be listed, and the percentages of subjects receiving each concomitant medication/treatment will be tabulated.

Dietary changes will be provided in listings, and, depending on the observed results, may be summarized in tables.

8.9 Pharmacokinetics

Pharmacokinetics will be analyzed for the PK Analysis Set. C_{max} will be recorded from direct observation. C_{max} will be summarized by dose of sebelipase alfa, if applicable.

8.10 Exploratory Biomarker Analysis

Potential disease-related biomarkers will be listed and observed values and changes and/or percent changes from baseline will be summarized at available timepoints.

8.11 Other Statistical Issues

8.11.1 Significance Levels

No formal hypothesis tests are planned. P-values, when presented, will be based on a 2-sided alpha of 0.05 and are intended to guide clinical judgment and interpretation of the data.

8.12 Subgroup Analyses

The impact of ADAs on safety, efficacy, PK, and PD endpoints will be explored descriptively. As subject numbers permit, other subgroup analyses of interest may be performed. These may include, but are not limited to age, gender, and race.

8.13 Missing or Invalid Data

All data will be analyzed as they were collected in the database.

8.14 Interim Analysis

No formal statistical hypothesis is planned to be tested in this protocol; therefore, no formal interim analyses are planned. Interim assessments of accumulating safety data will be performed as discussed in Section 7.5.

9 Data Handling and Record Keeping

9.1 Confidentiality

Information about study subjects will be kept confidential and managed according to the requirements of applicable local regulations.

9.2 Source Documents

Source data is all information, original records of clinical findings, observations, or other activities in a clinical trial necessary for the reconstruction and evaluation of the trial. Source data are contained in source documents. Examples of these original documents, and data records include: hospital records, clinical and office charts, laboratory notes, memoranda, subjects' diaries or evaluation checklists, pharmacy dispensing records, recorded data from automated instruments, copies or transcriptions certified after verification as being accurate and complete, microfiches, photographic negatives, microfilm or magnetic media, x-rays, subject files, and records kept at the pharmacy, at the laboratories, and at medico-technical departments involved in the clinical trial.

9.3 Case Report Forms

Required data for this study will be captured on eCRFs via electronic data capture (EDC) unless otherwise specified in this document. Except for data points for which the protocol or SOM indicates that the eCRF may serve as source documentation, data are to be obtained from the subject's source documents and then entered into the eCRF by authorized site personnel. Clinical data that are not recorded on the eCRF will be captured and transferred to the Sponsor or its designee.

9.4 Records Retention

It is the Investigator's responsibility to retain study essential documents for at least 2 years after the last approval of a marketing application in their country and until there are no pending or contemplated marketing applications in their country or at least 2 years have elapsed since the formal discontinuation of clinical development of the investigational product. These documents should be retained for a longer period if required by an agreement with the Sponsor. In such an instance, it is the responsibility of the Sponsor to inform the Investigator/institution as to when these documents no longer need to be retained.

10 Study Monitoring, Auditing, and Inspecting

10.1 Study Monitoring Plan

This study will be monitored according to the study monitoring plan. The Investigator will allocate adequate time for such monitoring activities. The Investigator will also ensure that the monitor or other compliance or quality assurance reviewer is given access to all the above noted study-related documents and study related facilities (e.g. pharmacy, diagnostic laboratory, etc.), and has adequate space to conduct the monitoring visit.

10.2 Auditing and Inspecting

The Investigator will permit study-related monitoring, audits, and inspections by the IRB/IEC, the Sponsor, government regulatory authorities, and quality assurance groups of all study related documents (e.g. source documents, regulatory documents, data collection instruments, study data etc.). The Investigator will ensure the capability for inspections of applicable study-related facilities (e.g., pharmacy, diagnostic laboratory, etc.).

Participation as an Investigator in this study implies acceptance of potential inspection by government regulatory authorities and applicable compliance and quality assurance offices.

11 Ethical Considerations

This study is to be conducted according to US and international standards of GCP (FDA Title 21 part 312 and ICH guidelines), applicable government regulations and Institutional research policies and procedures.

This protocol and any amendments will be submitted to a properly constituted IRB/IEC, in agreement with local legal prescriptions, for formal approval of the study conduct. The decision of the IRB/IEC concerning the conduct of the study will be made in writing to the Investigator and a copy of this decision will be provided to the Sponsor before commencement of this study. The Investigator should provide a list of IRB/IEC members and their affiliate to the Sponsor.

Each subject's parent or legal guardian for this study will be provided a consent form describing this study and providing sufficient information for the subject's parent or legal guardian to make an informed decision about their child's participation in this study. This consent form will be submitted with the protocol for review and approval by the IRB/IEC for the study. The formal consent of a subject, using the IRB/IEC-approved consent form, must be obtained before that subject undergoes any study procedure. The consent form must be signed by the subject's parent or legal guardian, and the Investigator-designated research professional obtaining the consent.

Any changes in the study protocol, such as changes in the study design, objectives or endpoints, inclusion and exclusion criteria, and/or procedures (except to eliminate an immediate hazard) will be implemented only after the mutual agreement of the Investigator and the Sponsor or designee. All protocol changes must be documented in protocol amendment(s). Protocol amendment(s) must be signed by the Investigator and approved by the IRB/IEC prior to implementation. Any changes in study conduct that result from a pending amendment will be considered protocol deviations until IRB/IEC approval is granted. Documentation of IRB/IEC approval must be returned to the Sponsor or designee.

12 Clinical Study Report and Publication Plan

A clinical study report will be produced after all subjects have reached 12 months of age or have died or withdrawn from the study, and will include all available subject data through 12 months of age or the date of death or early withdrawal. A final clinical study report will be produced after study completion, and will include cumulative subject data for the entire period of treatment in the study. A coordinating Investigator will be designated to review and sign the completed clinical study reports.

It is intended that the results from this research will be submitted to a peer-reviewed medical publication, once the study is completed, regardless of the outcome.

13 References

Appendix A: Schedule of Assessments

	Screening	Screening Treatment Phase [*]																
Assessments	Day -21 to Day -1	W 0 ¹⁰	W 1	W 2	W 3	W 4	W 5	W 6	W 7	W 8	W 9	W 10	W 11	W 12	W 13	W 14	W 15	W 16
		± 2 days	± 2 days	± 2 days	± 2 days	± 2 days	± 2 days	± 2 days	± 2 days	± 2 days	± 2 days	± 2 days	± 2 days	± 2 days	± 2 days	± 2 days	± 2 days	± 2 days
Informed Consent	Х						-											
Inclusion/Exclusion	Х	Х																
Medical/Family History	Х																	
Physical Exam ²	Х				Х						Х						Х	
Anthropometrics ³	Х	Х	Х	Х	Х	Х	Х	Х	Х	Х	Х	Х	Х	Х	Х	Х	Х	Х
Vital Signs ⁴	Х	Х	Х	Х	Х	Х	Х	Х	Х	Х	Х	Х	Х	Х	Х	Х	Х	Х
12-lead ECG	Х	If clinically indicated																
Denver II	Х																	
Abdominal Ultrasound		Х												Χ				
Abdominal MRI ⁵	X															Χ		
Clinical LabTests ^{6, 7}	Х	XP	XP	XP	XP	XP				XP								
Exploratory Biomarkers ⁷	X			Х						Х				Χ				X
DNA Sample (subject) ^{7, 8}	X																	
DNA Sample (parents)	X																	
PK Sample ^{7, 9}		X'																
DBS LAL Activity 7	X																	
Sebelipase Alfa Dosing ¹		Х	Х	Х	Х	Х	Х	Х	Х	Х	Х	Х	Χ	Х	Х	Х	Х	Х
Anti-drug Antibody 7	X X X X X X X X X X X X X X X X X X X								X									
Adverse Events		CONTINUOUS																
Concomitant Therapies	CONTINUOUS																	

^{*} All visits will be calculated from Week 0; consecutive infusions must be administered at least 5 days apart. Day 0 assessments do not need to be repeated if they have been conducted within the 3 days prior to Screening

P Pre-dose

- 1 For the subjects who are stable enough to be treated on an outpatient basis, safety follow-up assessments for AEs will be conducted by telephone 24 hours following the first 2 infusions of 1 mg/kg qw, and 3 mg/kg qw
- 2 All physical examinations will include liver, spleen, and lymph node assessments and digital photographs (full length and abdominal close up) (see Section 5.1.6).
- 3 Weight, recumbent length or height, and abdominal circumference will be measured at all visits; head and mid-upper arm circumference will be measured at Screening, Weeks 0, 4, 8, 12, and 16.
- 4 During infusion visits, vital signs will be measured pre-dose, every 15 (±5) minutes during the infusion, and every 30 (±10) minutes from 0 to 4 hours post-infusion (see Section 5.1.9).
- Abdominal MRI should be considered in subjects receiving general anesthesia and/or sedation for other procedures at the indicated timepoints. The Screening MRI may be obtained up to 8 weeks of treatment. There should be at least 3 months between each MRI. (Either a MRI or Ultrasound should be performed at a given timepoint.)
- 6 CBC/hematology, chemistry liver function tests, lipid panel, ferritin, urinalysis and coagulation studies (see Section 5.1.11). Prior to any dose change, serum lipid, serum liver, hematology, chemistry, ferritin, and hs-CRP shall be obtained. Serum lipid and serum liver assessments should be taken 4, 8, and 12 weeks following any study drug or lipid lowering medication change.
- 7 If blood volume is limited, refer to Section 5.1.11 for tiered assessments.
- 8 DNA sample should be collected at Screening or at the earliest possible visit thereafter based on blood volume threshold, unless a stored DNA sample is already available for the subject.
- 9 Refer to Section 5.1.14 for PK sampling timepoints
- 10 If the screening labs were performed within 2 days of Week 0 then the Week 0 labs do not need to be performed.

Page 63 of 66

ALEXION PHARMACEUTICALS, INC. PROPRIETARY AND CONFIDENTIAL:
DO NOT COPY OR DISTRIBUTE WITHOUT PERMISSION

LAL-CL08 Protocol Amendment 3.0 08 December 2015

Schedule of Assessments: Week 17 through Study Completion*

											epeating	Annually	Follow-up/			
	W 17	W 18	W 19	W 20	W 21	W 22	W 23			Every Week	Every Month	Every 2 Months (8 weeks)	Every 3 Months (12 weeks)	Every 6 Months (24 weeks)	(Week 48, Week 96, Week 144)	Early Withdrawal
	± 2 days	± 2 days	± 2 days	± 2 days	± 2 days	± 2 days	± 2 days	± 2 days	study	± 2 days	± 2 days	± 2 days	± 5 days	±15 days	±15 days	30 (+7) days
Physical Exam ¹	days	days	days	X	days	days	days	X	of s	dayo	dayo	dayo	X	days	dayo	X
Anthropometrics				Х				Х	end o		X ⁶		X ⁶			Х
Vital Signs ²	Х	Х	Х	Х	Х	Х	Х	Х	l e	Х						
12-lead ECG			ŀ	f clinicall	y indica	ted			until		If clinically indicated					
Denver II								Х	าร					Х		Х
Abdominal Ultrasound								Х	essments						Х	
Abdominal MRI								X ⁷	ess						X ⁷	
Liver Biopsy									Asse						Х	
Clinical Laboratory Assessments ^{3, 4}				Χ ^P				Χ ^P				X ^{8,P}	X ^{8,P}			Х
Exploratory Biomarkers ³								Х	Repeating					Х		Х
PK Sample ^{3, 5}						Х			1 -						X_{g}	
Sebelipase Alfa Infusion ¹⁰	Х	Х	Х	Х	Х	Х	Х	Х		Х						
Anti-drug Antibody				Х				Х					Х			Х
Adverse Events									(CONTINU	JOUS					
Concomitant Medications/ Therapies		CONTINUOUS														

^{*} All visits will be calculated from Week 0; consecutive infusions must be administered at least 5 days apart.

P Pre-dose

- 1 All physical examinations will include liver, spleen, and lymph node assessments. In addition, digital photographs (full length and abdominal close up) will be obtained at Weeks 20 and 24 and annually thereafter.
- 2 During infusion visits, vital signs will initially be measured pre-dose, every 15 (±5) minutes during the infusion, and every 30 (±10) minutes from 0 to 4 hours post-infusion (see Section 5.1.9). After a year of treatment with no IARs, the post-infusion monitoring period may be shortened from 4 hours to 2 hours.
- 3 If blood volume is limited, refer to Section 5.1.11 for tiered assessments.
- 4 CBC/hematology, chemistry, liver function tests, lipid panel, ferritin, urinalysis and coagulation studies, (see Section 5.1.11). Prior to any dose change, serum lipid, serum liver, hematology, chemistry, ferritin and hs-CRP shall be obtained. Serum lipid and serum liver assessments should be taken 4, 8, and 12 weeks following any study drug or lipid lowering medication dose change.
- 5 Refer to Section 5.1.14 for PK sampling timepoints.
- 6 Weight will be measured at all visits; Recumbent length or height, and abdominal circumference will be measured at every 3 month visits; head and mid-upper arm circumference will also be measured at all every 3 month visits through Week 96
- 7 Abdominal MRI should be considered in subjects receiving general anesthesia and/or sedation for other procedures. The MRI may be conducted at any time from Week 24 through Week 32, and then annually, and should be scheduled at least 3 months after the preceding MRI assessment.
- 8 Repeating assessments will be performed every 2 months through Week 48 and every 3 months thereafter until study completion.
- 9 PK samples will be collected only at the first annual assessment (Week 48).
- 10 Subjects who are on treatment for at least 96 weeks and have been on a stable dose for at least 24 weeks, may transition to an every other week dosing schedule at the same dose they received on the weekly dosing schedule at the discretion of the PI with Sponsor consultation.

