4.8 Subject Recruitment and Screening

Subjects may be recruited into the study directly from the Investigators' or sub-investigators' clinical practices, or referred to the investigative sites from other clinics. Information about the study will be posted on the http://clinicaltrials.gov/ and https://www.clinicaltrialsregister.eu/websites.

Subject screening should occur between 0 and 21 days prior to the infusion at Week 0 (Day 0). Prior to any screening procedures, a subject needs to be registered with the Sponsor.

5 Schedule of Assessments and Study Procedures

The schedule of assessments, Screening through Follow-up, is presented in Appendix A. All visits will be calculated from Week 0; consecutive infusions must be administered at least 5 days apart. Additional details regarding the visit schedule and the timing of study procedures are provided in the Study Operations Manual (SOM).

Subjects who are clinically stable enough to tolerate general anesthesia may be considered for central line placement for long-term vascular access, in accordance with institutional guidelines. Magnetic resonance imaging (MRI) should be considered for subjects receiving general anesthesia and/or sedation for central line placement or for other procedures (see Section 5.1.8).

Subjects who are medically stable, as determined by the Investigator, may transfer to a local medical center for long-term treatment, contingent upon the local medical center having been approved and having secured the required regulatory, IRB/IEC, and Sponsor approvals. Scheduled study assessments may also be performed at a local medical center with access to the appropriate facilities and expertise.

Local analgesic cream (e.g., eutectic mixture of local anesthetics) will be allowed at least 20-30 minutes (or according to applicable institutional guidelines) prior to IV placement or blood sampling.

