5.1.8 Abdominal MRI

Abdominal MRIs should be considered at the timepoints specified in Appendix A to provide a more accurate quantification of liver and spleen volume.

Abdominal MRIs are considered optional in this study. Investigators are encouraged to obtain abdominal MRIs in subjects receiving general anesthesia and/or sedation for other procedures at a scheduled imaging timepoint. To allow flexibility in scheduling MRIs, a broad time window is given for each MRI assessment in Appendix A. For example, the baseline MRI may be obtained at any time from Screening through the Week 0 study visit.

Because MRI can provide important information on liver and spleen volume that can be related to expected normal values abdominal MRIs should be obtained during the treatment phase, where feasible, even if a subject did not provide a baseline MRI.

All imaging scans will be acquired and the results interpreted by a magnetic resonance technician or other qualified individual using standardized imaging protocols.

Refer to the Imaging Manual for instructions on image acquisition and analysis.

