6.4 Preparation and Administration of IMP

6.4.1 Preparation of IMP

The infusion bag (or syringe) containing sebelipase alfa will be prepared just prior to the start of infusion administration. Prior to preparation of the infusion, the vials of study drug will be visually inspected. The solution should not be used if it contains foreign particulate matter or is discolored. The solution may be used if a small number of visible translucent to opalescent or white amorphous or threadlike particles are present in the vial. The contents should NOT be warmed using a microwave or other heat source. Sebelipase alfa is a protein and will be handled and mixed gently to prevent foaming.

If subject's weight cannot reliably be obtained on the morning of the infusion then the subject's most recent weight measurement within 7 days, rounded to the nearest 0.1 kg, will be used for calculating the volume of study drug to be withdrawn from the vial(s) to prepare the infusion.

Sebelipase alfa should be diluted to a concentration of 0.1 to 1.5 mg/ml for infusion. Refer to the IMP manual for detailed instructions regarding preparation

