8.1 General Considerations

All data will be presented in listings; summary tables and graphs will be provided, as appropriate. Unless otherwise noted, tabulations for efficacy endpoints will be presented for subjects in the Full Analysis Set (FAS). Descriptive summary statistics (n, mean, median, standard deviation, minimum and maximum) will be calculated for the continuous variables. Shift tables and/or frequencies and percentages will be produced for the categorical variables. When percentages are reported, the number of treated subjects will be used as the denominator, unless otherwise noted. As appropriate, 95% two-sided confidence intervals (CIs) will be calculated around the estimates based on the exact binomial distribution for binomial endpoints and the t-distribution for continuous endpoints.

Baseline will be defined as the last measurement prior to the first infusion of sebelipase alfa. (Note: For exploratory analyses, the first available measurement after initiation of treatment may be used as baseline if a pretreatment measurement is unavailable.) In order to facilitate comparison with literature, survival analyses will be presented with subject birth date as "time 0"; analyses of other endpoints over time will consider date of first dose as "time 0".

Details of the planned analyses and statistical methodologies will be provided in a separate Statistical Analysis Plan.

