#### 9.4.8 Definition of Baseline Values and Change from Baseline

#### 9.4.8.1 Baseline

Baseline is defined as the last available assessment prior to the start of the first infusion of sebelipase alpha. If any Baseline laboratory analyte is evaluated at both the local and the central laboratory, then the central laboratory results will be used for analysis.

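### The Day 0 waiver in Appendix A counts from Screening instead of Week 0, so baseline length and circumferences can be up to 21 days old and baseline ultrasound up to 24

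*Protocol*

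**What the plan says.** The asterisk footnote to the Screening-to-Week-16 table in Protocol Appendix A reads: "Day 0 assessments do not need to be repeated if they have been conducted within the 3 days prior to Screening". The same table places Screening at Day -21 to Day -1, and Protocol Section 4.8 likewise allows it up to 21 days before the Week 0 infusion.

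Footnote 10 of that table, attached to the Week 0 column, gives laboratory tests their own rule: "If the screening labs were performed within 2 days of Week 0 then the Week 0 labs do not need to be performed".

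Baseline has no age limit in either document. Protocol Section 8.1: "Baseline will be defined as the last measurement prior to the first infusion of sebelipase alfa". SAP Section 9.4.8.1: "Baseline is defined as the last available assessment prior to the start of the first infusion of sebelipase alpha". SAP Section 7.2 says the same for safety data.

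For preparing the infusion, Protocol Section 6.4.1 calls for a weight from that morning. Failing that, "the subject's most recent weight measurement within 7 days, rounded to the nearest 0.1 kg, will be used".

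**The concern.** A waiver of this kind normally spares an infant a repeat measurement when a recent one exists. As worded, it does the reverse. A value from Day -24, three days before a Day -21 Screening, qualifies. A value taken at a Day -1 Screening visit does not, because it was not taken before Screening. The qualifying value would also normally predate consent: Protocol Section 5.1.1 requires signed consent before screening procedures begin, and Section 11 before any study procedure. Non-study data could therefore displace a protocol measurement.

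This matters because each infant is his or her own reference. There is no comparator and enrolment stops at 10, so change from baseline carries the growth and organ-size results. If Week 0 is skipped, up to three untreated weeks fall between the baseline value and the first dose, and whatever happened in them is reported as change on treatment. Measures exposed are the length-for-age, head-circumference and arm-circumference z-scores, the length component of weight-for-length, the stunting and wasting indicators at baseline, abdominal circumference, and ultrasound liver and spleen size.

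The direction is not fixed. Growth arrest before dosing would lower the age-standardised score and count against treatment; a gain from nutritional support would count in its favour. With so few infants these need not cancel.

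**Working it through.** The documents state no figure for the age of baseline, so there is none to reproduce. The check is a day count plus a reading of which assessments Appendix A schedules at Screening and at Week 0.

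**Inputs**
- Earliest Screening: Day -21 (Appendix A; Section 4.8).
- Waiver window: 3 days before Screening (Appendix A, asterisk footnote).
- Baseline: last value before first infusion, with no maximum age (Protocol 8.1; SAP 9.4.8.1).
- Head and arm circumference: "head and mid-upper arm circumference will be measured at Screening, Weeks 0, 4, 8, 12, and 16". Weight, length and abdominal circumference are taken at every visit in this table.
- Ultrasound: marked at Week 0, not at Screening.
- Physical examination and MRI: marked at Screening, not at Week 0.

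**Day count under the literal footnote**
- Scheduled at both Screening and Week 0: if Week 0 is waived, the Screening value is the last one before dosing. Oldest age = 21 days.
- Scheduled at Week 0 only: if Week 0 is waived, the qualifying value precedes Screening. Oldest age = 21 + 3 = 24 days, or 24 / 7 = 3.4 weeks. With Screening on Day -1 and the same 3-day lead, it is 1 + 3 = 4 days.
- With the waiver counted from Week 0, a waived assessment is at most 3 days old.

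| Assessment | Screening | Week 0 | Oldest baseline, literal footnote | Waiver anchored on Week 0 |
|---|---|---|---|---|
| Length; head, arm and abdominal circumference | yes | yes | 21 days | 3 days |
| Ultrasound liver and spleen | no | yes | 24 days | 3 days |
| Weight | yes | yes | 7 days (Section 6.4.1) | 3 days |
| Palpation of liver, spleen, nodes | yes | no | 21 days, not due to this footnote | unchanged |
| MRI | yes | no | own timing rules | unchanged |
| Laboratory tests | yes | yes | footnote 10: waiver within 2 days of Week 0 | unchanged |

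The weight row assumes that the dosing weight is recorded as study data. The laboratory row assumes that the specific rule in footnote 10 overrides the general asterisk footnote.

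MRI timing is a separate matter. Section 5.1.8 says "the baseline MRI may be obtained at any time from Screening through the Week 0 study visit", while the Appendix A MRI footnote allows the Screening scan up to 8 weeks into treatment. Those two statements need reconciling, but the Day 0 waiver does not bear on them.

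Vital signs are compared with pre-infusion values, and survival runs from birth or first dose, so neither uses a waived Day 0 value as its reference.

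**The case against.** The strongest reply is that nobody would apply the footnote as written. Speaking of an assessment being repeated suggests that the author meant a Screening assessment done shortly before Day 0. The pre-consent difficulty makes the literal reading awkward to operate. The clause is permissive, these infants are enrolled because they need urgent intervention, and 21 to 24 days is therefore a worst case. The Study Operations Manual, which is not available here, may settle the timing. The study is descriptive and lists data by subject, so a stale value could be found from its date.

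Much of that is fair. A slip of the pen is plausible, and how sites read the footnote is unknown. But nothing in the protocol or SAP corrects the wording, and neither baseline definition would reject an old value.

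It is also fair that footnote 10 can stand beside a general rule as a specific one. The 2-day and 3-day windows need not be merged; only the mismatch in anchor is a fault.

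A reader might infer a loss of about a tenth of body weight: at 5 g/kg/day, 21 days gives 21 × 5 = 105 g/kg (10.5%) and 24 days gives 24 × 5 = 120 g/kg (12%). The documents do not support this. Section 6.4.1 limits the dosing weight to 7 days, which at the same rate is 7 × 5 = 35 g/kg (3.5%). Moreover, 5 g/kg/day is a dose-escalation criterion for infants already on treatment (Section 3.1.1.1), not an untreated growth rate, and Section 3.2.2.2 describes growth as typically ceasing in this disease.

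**Conclusion.** The footnote is wrong as written and should be corrected. Followed literally, it permits a baseline up to 21 days old for length and for head, mid-upper arm and abdominal circumference, and up to 24 days old for ultrasound liver and spleen size, against 3 days if anchored on Week 0. These are upper limits. They assume that Screening falls on Day -21, that a site uses the waiver as worded, and that no other measurement is taken before dosing. The resulting bias in z-score or organ-size units cannot be computed, because the documents give no pre-treatment rate of change.

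A reader might infer that every change-from-baseline endpoint is compromised, or that examination and all imaging are. The schedule does not bear that out. The palpation examination and MRI have no Week 0 entry to waive, laboratory endpoints such as AST, ALT and ferritin follow footnote 10, and weight, vital signs and survival have their own references. What is exposed is part of the secondary growth analysis and the exploratory ultrasound measures; the primary safety objective is largely outside its reach.

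**What to change.** In the Appendix A asterisk footnote, replace the anchor *Screening* with *Week 0 (Day 0)*, keeping the 3-day window, and add that footnote 10 governs laboratory tests. This costs one phrase and one clause in an amendment.

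If dosing has already begun, the wording can no longer change the data. In that case, list the study day of each baseline value beside the value for length, the circumferences and ultrasound, so that stale baselines can be identified and the affected changes read accordingly. SAP Section 9.4.7 already derives study day, so this costs one listing column.
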